9.0 Concomitant and Prohibited Therapy

Concomitant therapy includes any prescription medications or over the counter preparations used by a patient between the 7 days preceding the screening evaluation and the treatment discontinuation visit. If the patient is taking any prohibited medications as of the day of consent, alternatives will be discussed with the patients prior to initiating treatment on study. For agents known to prolong QT interval, if the principal investigator and/or attending physician deems the risk for QT prolongation to be low, continuation may be allowed if it is considered in the patient's best interest. Increased cardiac monitoring may be done in these circumstances for patient safety per physician's discretion as standard of care.

Patients who use hormone-replacement therapy, prophylactic or therapeutic anticoagulation therapy (such as low-molecular-weight heparin or warfarin at a stable dose level) should continue their use. However, hormone-replacement therapy should be discontinued if the patient is HR-positive.

All concomitant medications will be documented in medical record as standard of care only, and will not be collected for this study.

Any other anti-cancer agents and agents listed below are prohibited.

9.1 Prohibited Concomitant Therapy and Cautions for Capmatinib Use:

There is no contraindication for the use of Capmatinib. But there are some drug interactions identified:

- P-gp Inducers**

Capmatinib is a substrate for P-gp. Strong P-gp inducers may have the potential to decrease Capmatinib exposure. Concomitant use of strong P-gp inducers (e.g., carbamazepine, phenytoin, rifampicin, and St. John's wort) should be avoided.

- P-gp Substrates**

Multiple administrations of Capmatinib HCl hydrate 500 mg once daily for 8 days had a mild effect on the PK of the sensitive P-gp substrate dabigatran etexilate, increasing its exposure by approximately 50% based on the AUC. Monitoring the clinical effects of P-gp-dependent substances with a narrow therapeutic index (e.g., digoxin) is recommended during co-administration with Capmatinib.

- BCRP Substrates**

Capmatinib can inhibit the transport of sensitive substrates of BCRP. Monitoring the clinical effects of sensitive BCRP substrates is recommended during co-administration with Capmatinib.

- Metformin**

Based on in vitro data, Capmatinib and its metabolite may have the potential to increase the AUC of co-administered metformin in humans, through inhibition of its renal excretion mediated via OCT1 and OCT2, and MATE1 and MATE2. Monitoring of the

effect of metformin is recommended during co-administration with Capmatinib, which is not contraindicated.

- **Proton Pump Inhibitor**

The solubility of capmatinib is pH-dependent. The [CINC280A2101] study was a clinical drug-drug interaction study investigating the effect of the proton pump inhibitor, rabeprazole, on a single dose of 600 mg capmatinib tablet in healthy subjects.

Rabeprazole treatment resulted in a modest reduction in the extent of capmatinib absorption with a 37.5% decrease in Cmax and a 25.2% decrease in AUCinf.

9.2 Prohibited Concomitant Therapy for Neratinib use:

1. Agents known to be strong cytochrome P450 (CYP) 3A4 inducers or inhibitors, such as: phenobarbital, phenytoin, primidone, rifampin, dexamethasone, and oral contraceptives.

Patients should also avoid grapefruit and herbal remedies, including, but not limited to St. John's Wort.

2. Chronic immunosuppressive therapies including systemic corticosteroids. Steroids given for physiological replacement, as anti-emetics or inhaled as well as short course of oral/topical steroids given for allergic reactions or asthma flares are allowed.
3. P-glycoprotein (P-gp) Substrates: Concomitant use of neratinib with digoxin, a P-gp substrate, increased digoxin concentrations. Increased concentrations of digoxin may lead to increased risk of adverse reactions including cardiac toxicity. Refer to the digoxin prescribing information for dosage adjustment recommendations due to drug interactions. Neratinib may inhibit the transport of other P-gp substrates (e.g., dabigatran, fexofenadine).
4. Drugs that have interactions that affect neratinib (see Table 8 Drug Interactions That Affect Neratinib).

10.0 Common Toxicity and Dose Modification

10.1 Neratinib Dose Modifications and Management – General Toxicities

For toxicities deemed to be related to neratinib, follow Table 10.

Table 10: Neratinib Dose Modifications and Management – General Toxicities*

Severity of Toxicity [†]	Action
Grade 3	Hold NERLYNX until recovery to Grade ≤ 1 or baseline within 3 weeks of stopping treatment. Then resume NERLYNX at the next lower dose level.
Grade 4	Discontinue NERLYNX permanently.

* Refer to Tables 13, 14 below for management of diarrhea and hepatotoxicity

† Per CTCAE v5.0

10.2 Management of Diarrhea

Diarrhea is a commonly occurring toxicity. Monotherapy with neratinib has a median time of 3 days to onset of diarrhea. With combination therapy, it is anticipated that diarrhea may occur

earlier. For the majority of patients, diarrhea subsides after about 2 weeks. Therefore, intensive prophylactic measures begin at the start of therapy. If diarrhea occurs despite prophylaxis, treat with additional antidiarrheals, fluids and electrolytes as clinically indicated. Additionally, based on results from the CONTROL clinical trial, the neratinib dose will be escalated to the assigned target dose during the 1st cycle of treatment (29).

Patients **must** be instructed to:

- start prophylactic antidiarrheal therapy (see below) on day 1, with the first dose of neratinib
- continue prophylactic therapy as directed
- promptly report diarrhea symptoms
- record the number of stools per day
- record each dose of antidiarrheal medicine taken each day
- report constipation *before* taking any laxatives or stopping antidiarrheal medication. Anti-diarrheal medication may be held for constipation at the discretion of the treating physician, but should be resumed if diarrhea recurs.

Intensive primary prophylaxis

Antidiarrheal medication (loperamide) must begin with the first dose of neratinib. Patients must take an initial dose of loperamide 4 mg p.o. with the first dose of neratinib, then followed by 4 mg TID for the first 14 days. After two weeks on study, patients will take loperamide PO 4 mg twice a day (BID) for the remainder of the first two cycle of neratinib. Thereafter, loperamide will be administered as needed throughout neratinib treatment, not to exceed 16 mg per day.

Table 11: Suggested Dosing Time

	7am	2pm	7pm	9pm
C1D1 through 28 days	Neratinib & Capmatinib with food**		Capmatinib	
	Loperamide 4mg***	Loperamide 4mg***		Loperamide 4mg***

** Neratinib and Capmatinib dose will be as assigned

*** After the first 14 days, loperamide 4 mg is to be taken twice a day through the first two cycle only of therapy (Day 56). Daily dose as needed (not to exceed 16 mg per day) for Days 56+ (Cycle 3 and beyond).

For Grade 2 diarrhea lasting \geq 5 days despite prophylactic medication, and higher grade (Grade 3 and 4), we recommend following the guideline as noted in below Table 12.

Table 12: Management Guideline for Neratinib-related Diarrhea

Severity of Diarrhea*	Action

 Grade 1 diarrhea [increase of <4 stools per day over baseline] Grade 2 diarrhea [increase of 4–6 stools per day over baseline] lasting \leq 5 days Grade 3 diarrhea [increase of \geq 7 stools per day over baseline; incontinence; hospitalization indicated; limiting self-care activities of daily living] lasting \leq 2 days 	
 Adjust antidiarrheal treatment Diet modifications Fluid intake of ~2 L should be maintained to avoid dehydration Once event resolves to \leq Grade 1 or baseline, start loperamide 4 mg with each subsequent NERLYNX administration

 Any grade with complicated features[†] Grade 2 diarrhea lasting longer than 5 days[†] Grade 3 diarrhea lasting longer than 2 days[†] 	
 Interrupt NERLYNX treatment Diet modifications Fluid intake of ~2 L should be maintained to avoid dehydration If diarrhea resolves to Grade 0–1 in one week or less, then resume NERLYNX treatment at the same dose. If diarrhea resolves to Grade 0–1 in longer than one week, then resume NERLYNX treatment at reduced dose (see Table 2) Once event resolves to \leq Grade 1 or baseline, start loperamide 4 mg with each subsequent NERLYNX administration

 Grade 4 diarrhea [life-threatening consequences; urgent intervention indicated] 	
 Permanently discontinue NERLYNX treatment

 Diarrhea recurs to Grade 2 or higher at 120 mg per day 	
 Permanently discontinue NERLYNX treatment

Note: Antidiarrheal treatment adjustment will be per physician's discretion. Examples of antidiarrheal treatment include but not limited to:

- Diphenoxylate 5 mg/Atropine Sulfate 0.05 mg (Lomotil): 2 tablets or 10 mL by mouth, 4 times per day, as needed. Maximum 8 tablets, or 40 mL per day.
- Colestipol: 2 grams by mouth twice per day. Colestipol should be taken at least 1 hour after and at least 4 hours before other oral medications.
- Tincture of Opium, 10 mg/mL: 6 mg (0.6 mL) 4 times per day, as needed.

Note: If grade 3 diarrhea reoccurs, the patient may maintain the same dose level of Neratinib or have dose reduced to the next lower dose (120 mg is the lowest dose level of Neratinib), per physician discretion. The patient may voluntarily come off the study at any time.

* Per CTCAE v5.0

† Complicated features include dehydration, fever, hypotension, renal failure, or Grade 3 or 4 neutropenia

‡ Despite being treated with optimal medical therapy

Stop Loperamide if no bowel movement for \geq 2 days per attending physician's discretion and resume the Loperamide as instructed if any signs and symptoms of abdominal cramping, loose stool and diarrhea occurs: take 2 pills of Loperamide immediately, then 1 pill of Loperamide with each subsequent episode of diarrhea, which is not to exceed 8 pills of Loperamide in 24

hours. If diarrhea persists, take Lomotil and/or other antidiarrheal medications as needed per standard of care per attending physician's discretion. Resume adjusted dosage of Loperamide as per attending physician's discretion to manage the diarrhea and Loperamide induced constipation.

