4.1 Phase 1b – Dose Escalation of Neratinib with Capmatinib

This phase of the study will employ the Bayesian optimal interval (BOIN) design (Liu and Yuan, 2015 Yuan et al., 2016) (24, 25), with the 3+3 design run-in, to find the MTD. The BOIN design is implemented in a simple way similar to the traditional 3+3 design, but is more flexible and possesses superior operating characteristics that are comparable to those of the more complex model-based designs, such as the continual reassessment method (CRM) (Zhou et al., 2018) (26). The maximum sample size for dose escalation is 18. Patients are treated in cohorts of 3, beginning with Neratinib PO dose level 1 (120 mg, Dose 1-7, 160 mg, through end of treatment, see Table 2) in combination with Capmatinib PO level 1 (400 mg, see Table 3), with a maximum of 12 patients per dose. The target toxicity rate for the maximum tolerable dose (MTD) is 25%.

This trial was designed and will be conducted using the shiny app “BOIN” (BOIN V2.6.3.0) available at <http://www.trialdesign.org..> Further information about the design can be found in Section 13.

Table 2. Phase Ib Neratinib PO dose levels, in combination of Capmatinib PO.

Dose Level	1	2	3
Neratinib PO	120 mg, Dose 1-7, 160 mg, through end	120 mg, Dose 1-7, 160 mg, Dose 8-14, 200 mg, through end	120 mg, Dose 1-7, 160 mg, Dose 8-14, 240 mg, through end
Capmatinib PO	400 mg b.i.d.	400 mg b.i.d.	400 mg b.i.d.

Table 3 : Fallback Dose levels.

	Dose level -1	Dose level -2
Neratinib PO	120 mg, Dose 1-7, 160 mg, through end	120 mg, Dose 1-7, through end
Capmatinib PO	300 mg b.i.d.	200 mg b.i.d.

Note: dose reduction should be based on the worst toxicity demonstrated at the last dose.

Dose reduction below 200 mg is not allowed

This protocol will be monitored by IND Office and safety data will be reviewed by IND Office after all subjects in a given cohort have completed the DLT assessment period (Cycle 1 and 2, total 56 days) and the dose level for next cohort will be determined based on the results.

Prior to advancing/changing dose levels, a cohort summary will be completed and submitted to the IND Medical Monitor for review and approval.

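### For a patient on dose level 1, the neratinib reduction step is internally inconsistent: Table 12 cites Table 2, which lists nothing below level 1, and level -1 in Table 3 leaves neratinib unchanged

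*Combined protocol and SAP*

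**What the plan says.** **Reduction instructions for neratinib.** In Section 10.2, Table 12 covers complicated or prolonged diarrhea. If it takes longer than a week to settle, the instruction is "then resume NERLYNX treatment at reduced dose (see Table 2". In Section 10.1, Table 10 says for Grade 3 toxicity: "Then resume NERLYNX at the next lower dose level". In Section 10.4, Table 13 gives the same kind of instruction for Grade 3 liver toxicity. Neither Table 10 nor Table 13 names the table that defines the levels. A note under Table 12 states that "120 mg is the lowest dose level of Neratinib", and one row of that table deals with diarrhea recurring at that dose.

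**The tables of levels (Section 4.1).** The first is headed "Table 2. Phase Ib Neratinib PO dose levels, in combination of Capmatinib PO". Its neratinib entries are:
- level 1: "120 mg, Dose 1-7, 160 mg, through end"
- level 2: "120 mg, Dose 1-7, 160 mg, Dose 8-14, 200 mg, through end"
- level 3: "120 mg, Dose 1-7, 160 mg, Dose 8-14, 240 mg, through end"

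Capmatinib is 400 mg b.i.d. at all three. Table 3, titled "Fallback Dose levels", adds level -1, with the level 1 neratinib schedule and capmatinib 300 mg b.i.d., and level -2, with neratinib 120 mg and capmatinib 200 mg b.i.d. A note beneath it rules out reduction below 200 mg and names no drug.

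**Related rules.** Section 7.3 says that when a toxicity is attributed to one study drug, that drug may be held while the other is given as scheduled; the held drug is then resumed and, if indicated, reduced under Section 10. Capmatinib has its own reduction table (Table 14, Section 10.5.1). Neratinib has none.

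**The concern.** Level 1 is where the first cohort starts, and it may be the dose carried into phase II. A physician who must reduce neratinib for a level 1 patient and follows the Table 12 reference finds no lower entry. Going on to the next listed level, in Table 3, the physician finds neratinib unchanged and the other drug lowered.

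The main stake is safety: the instruction is meant to reduce the drug held responsible. Permanent discontinuation is affected as well. Table 13 stops neratinib if the Grade 3 liver abnormality recurs despite one dose reduction, and it is unclear whether a move from level 1 to level -1 counts as one.

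There is also a statistical stake. If physicians resolve the ambiguity differently, patients recorded at the same level will have different neratinib exposure during the 56-day toxicity window and the 4-cycle response window (Section 13.2).

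**Working it through.** No sample size, power or error rate is involved, so the check is a level-by-level reading of Tables 2 and 3 against Tables 10, 12 and 13.

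**1. Each one-level step down (maintenance doses from Section 4.1)**

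| Step | Neratinib, mg daily | Capmatinib, mg b.i.d. | Lower level listed in | Neratinib lowered? |
|---|---|---|---|---|
| 3 to 2 | 240 to 200 | 400 to 400 | Table 2 | yes |
| 2 to 1 | 200 to 160 | 400 to 400 | Table 2 | yes |
| 1 to -1 | 160 to 160 | 400 to 300 | Table 3 | **no** |
| -1 to -2 | 160 to 120 | 300 to 200 | Table 3 | yes, together with capmatinib |

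Three of the four steps lower neratinib. The step from level 1 does not.

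**2. What each instruction gives a level 1 patient**
- Table 12 sends the reader to Table 2, where nothing lies below level 1. No dose results.
- Tables 10 and 13, read as the next listed level, lead to level -1. Neratinib stays at 160 mg and capmatinib falls, against Section 7.3.
- Tables 10 and 13, read as neratinib only, have no list of neratinib levels to refer to. The lowest level in Table 2 has 160 mg maintenance, whereas the note under Table 12 puts the lowest at 120 mg.

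**3. Other wording on the same point**
- The 200 mg floor under Table 3 names no drug. Applied to neratinib, it would contradict the 160 and 120 mg entries directly above it. The same note stands under capmatinib's Table 14, which suggests that it concerns capmatinib.
- The Table 10 footnote sends readers to Tables 13 and 14 for diarrhea and hepatotoxicity. Those subjects are in Tables 12 and 13; Table 14 is capmatinib.
- Section 7.2 says neratinib comes as 40 mg tablets, 3 to 6 daily: 3 × 40 = 120 mg and 6 × 40 = 240 mg. This range agrees with the note under Table 12 and with level 3.

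**4. How often level 1 matters (Table 19, the plan's four simulated scenarios)**

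| Scenario | Mean N | % treated at level 1 | Mean number at level 1 | % of trials selecting level 1 as MTD |
|---|---|---|---|---|
| 1 | 17.2 | 34.0 | 17.2 × 0.340 = 5.8 | 13.2 |
| 2 | 17.1 | 41.4 | 17.1 × 0.414 = 7.1 | 24.1 |
| 3 | 16.6 | 50.6 | 16.6 × 0.506 = 8.4 | 62.8 |
| 4 | 17.1 | 35.9 | 17.1 × 0.359 = 6.1 | 25.3 |

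Level 1 has the largest share of patients in scenarios 1 to 3. If it is selected, up to 29 phase II patients start there.

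**The case against.** The strongest reply is that a careful reader can work out what is meant. Tables 10 and 13 speak of resuming neratinib, not of moving the patient to another combination level, and Section 7.3 is drug-specific. The note under Table 12, its row on recurrence at 120 mg, the tablet range and Table 3 agree with one another, so an order of 240, 200, 160 and 120 mg can be inferred. Table 3 also has another evident purpose: levels -1 and -2 are cohort levels of the dose-finding design. They are simulated in Table 19, and Appendix 1 gives five doses with the third as the start. An unchanged neratinib dose is not in itself an error in such a step.

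Much of this stands. A reader might infer that the neratinib reductions cannot be followed at all, or that a patient with neratinib toxicity would necessarily stay on the same dose. The documents do not support either reading: Table 2 gives lower neratinib doses to patients on levels 2 and 3, level -2 is below level -1 for neratinib, and an order can be inferred.

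What the reply does not remove is that this order is nowhere stated as reduction steps. The one explicit cross-reference leads a level 1 patient to no dose, and the next listed level runs against Section 7.3. The existence of Table 14 shows that the plan treats explicit steps as necessary for the partner drug.

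**Conclusion.** The point holds as an internal inconsistency limited to the step down from level 1. It is not a flaw in the dose-finding algorithm, and no stopping boundary or error rate has been shown to change. A DLT counts regardless of how many doses were received (Section 7.3), so the effect on the toxicity and response results is a possibility and has not been quantified.

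Its reach is the set of level 1 patients who need a neratinib reduction. The documents do not allow that number to be estimated. A reader might size it from the Grade 3 diarrhea rate in Table 5, but that rate comes from 240 mg monotherapy without loperamide prophylaxis. This trial mandates prophylaxis and steps the dose up, and Table 12 reduces the dose only after complicated or prolonged diarrhea that takes more than a week to resolve. The Table 19 figures show only how many patients may be at level 1, and they rest on the plan's assumed toxicity scenarios.

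The matter is still worth correcting promptly, because it concerns a toxicity instruction at the starting dose.

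**What to change.** Reconcile Tables 2, 3, 10, 12 and 13 with Section 7.3:
- set out the neratinib reduction steps in a table of their own, separate from the combination cohort levels, as Table 14 does for capmatinib;
- point Tables 10, 12 and 13 to that table;
- correct the Table 10 footnote so that diarrhea and hepatotoxicity lead to Tables 12 and 13;
- state which drug the 200 mg floor under Table 3 concerns.

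The doses and steps are for the sponsor's clinical team to set; none is proposed here. The cost is one table, three cross-references, one footnote and one clarified note. Sample size, decision boundaries and simulations are unaffected.

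### For Grade 3 diarrhea that recurs at neratinib 120 mg per day, Table 12 says stop, the note beneath it allows the same dose, and no text says which governs (minor)

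*Combined protocol and SAP*

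**What the plan says.** Two instructions in Section 10.2 deal with diarrhea that comes back.

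- **Last row of Table 12.** Trigger: "Diarrhea recurs to Grade 2 or higher at 120 mg per day". Action: neratinib is discontinued permanently.
- **Note under Table 12.** "If grade 3 diarrhea reoccurs, the patient may maintain the same dose level of Neratinib", or go to the next lower dose, as the physician judges. A parenthesis adds that "120 mg is the lowest dose level of Neratinib".

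Section 10.2 introduces Table 12 as a guideline that it recommends following. The title of the table also calls it a guideline.

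Patients can be at 120 mg in three ways: during the first seven doses of most dose levels (for levels 1 and -1, "120 mg, Dose 1-7, 160 mg, through end"), throughout fallback level -2 ("120 mg, Dose 1-7, through end"), or after a reduction to the floor.

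The footnote to Table 10 in Section 10.1 says "Refer to Tables 13, 14 below for management of diarrhea and hepatotoxicity".

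**The concern.** A second Grade 3 episode at 120 mg per day falls under both the row and the note. The row requires a permanent stop. Because 120 mg is the floor, the note's step-down option is empty there, and the only dosing option it leaves is to continue at 120 mg. Two physicians who each follow protocol text could therefore stop or continue the drug in the same patient.

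What is at stake is consistent handling of a safety stop, for a toxicity that both study drugs share (Table 4). The note names the floor without adding a stop at that dose, so a physician who relies on it is not plainly misreading it.

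**Working it through.** No figure in the plan is in dispute, so the main check is a comparison of texts.

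**1. Where the two instructions overlap**

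| Recurrence | Last row of Table 12 | Note under Table 12 | Conflict? |
|---|---|---|---|
| Grade 2 at 120 mg | Stop permanently | Silent | No |
| Grade 3 at 120 mg | Stop permanently | Same dose allowed | **Yes** |
| Grade 4 at 120 mg | Stop permanently (the Grade 4 row also says so) | Silent | No |
| Grade 3 above 120 mg | Silent | Same dose or step down | No |

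The conflict is one cell: Grade 3 recurrence at 120 mg.

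**2. Whether other text settles it**

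- Section 7.3 says dose reductions follow Section 10, which leads back to the same table.
- Section 7.6 has no diarrhea-specific rule. Its intolerable-toxicity item rests on the investigator's judgment, and its sustained-toxicity item needs an interruption of more than 8 weeks.
- Section 10.1 defers diarrhea to other tables through the Table 10 footnote. That footnote is misnumbered: diarrhea is in Table 12, hepatotoxicity in Table 13, and Table 14 holds the capmatinib reduction steps. Even with the numbers corrected it would not rank the row against the note, so it is a separate clerical slip.
- Section 10.2 recommends Table 12 as a whole and gives no order between row and note.

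**3. Whether dose finding could be affected**

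Inputs: once-daily neratinib (7.2), a DLT window of 56 days (7.4), and at least 80% of scheduled doses for DLT evaluability (7.3).

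- Doses needed: 0.80 × 56 = 44.8, so 45.
- Doses that may be missed: 56 − 45 = 11.
- Stopping after 44 doses gives 44/56 = 78.6%, which is below 80%.

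A Phase Ib patient with no DLT whose neratinib is stopped at dose 44 or earlier is non-evaluable and is not counted in Table 18. The same patient continued under the note could stay evaluable.

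The path is narrow. A patient with any DLT counts whatever the number of doses taken (7.3). The duration triggers in Table 12 that interrupt neratinib are Grade 3 for more than 2 days and Grade 2 for more than 5 days. Both lie within the DLT criteria in 7.4, which are Grade 3 for at least 2 days and Grade 2 for at least 5 days. A patient brought down to 120 mg by those triggers within 56 days is therefore generally already a DLT. The routes to 120 mg without a DLT are level -2, the lead-in, complicated lower-grade diarrhea, a discretionary reduction after brief Grade 3 diarrhea, or a Grade 3 hematologic event.

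**4. Whether Phase II toxicity monitoring could be affected**

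Section 13.2 counts Grade 3 or higher toxicity over 2 cycles. A Grade 3 recurrence in that window counts whether neratinib is then stopped or continued.

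**5. The lead-in**

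The row does not say whether it covers the seven 120 mg doses at the start of levels 1, 2, 3 and -1. Level -2 has no lead-in, because 120 mg is its assigned dose. The case needs an episode and a recurrence within seven doses. Section 10.2 says "Monotherapy with neratinib has a median time of 3 days to onset of diarrhea" and expects earlier onset with the combination, so this is possible but uncommon by construction.

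**The case against.** The strongest reply is that the texts can be read together. The row names a dose and an action, while the note is general. A choice between staying and stepping down most naturally addresses patients who have a step left. Table 12 is also a recommended guideline, and Section 7.3 already gives the physician discretion to withhold drug, so some variation between physicians is foreseen. Much of this stands: the row is the better reading, and what is missing is one clause. It does not remove the point. The note addresses Grade 3 recurrence by name, and a permanent stop should not depend on an interpretive rule that the reader must supply.

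A reader might infer three stronger things, and the documents support none of them.

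- **That the conflict matters for dose finding, response or error rates.** Steps 3 and 4 show a narrow path to non-evaluability and no change in the Phase II toxicity count. Nothing links the conflict to ORR or to the error rates.
- **That many patients are affected because diarrhea is common.** The conflict needs recurrent Grade 3 diarrhea at 120 mg despite mandatory loperamide prophylaxis. The 39.8% Grade 3 rate in Table 5 comes from 240 mg monotherapy without that prophylaxis, and it is not a recurrence rate.
- **That lead-in patients should be exempt from the row.** On its face the row covers any patient at 120 mg. An exemption would be new clinical policy and would loosen a safety stop.

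**Conclusion.** The point holds as a minor internal inconsistency. For Grade 3 diarrhea recurring at neratinib 120 mg per day, the row requires a permanent stop, the note permits the same dose, and no text says which governs. The row is the natural reading, within a table offered as a recommended guideline.

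The size in patients is unknown, because the documents give no recurrence rate at 120 mg. No material effect on dose finding, Phase II toxicity monitoring, ORR or error rates is claimed. The conclusion assumes only that the note applies at every dose, as its wording does not limit it.

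**What to change.** Limit the note to patients receiving more than 120 mg per day, for example by adding an exception that at 120 mg per day neratinib is permanently discontinued. The cost is a wording amendment, with no added patients or procedures. The downside is that a patient with Grade 3 recurrence at 120 mg loses the discretionary option to continue, which the row already removes.

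The sponsor should also decide, and state, whether the row applies during the 120 mg lead-in. No exemption is proposed here.

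Separately, as a clerical correction, the Table 10 footnote should point to Tables 12 and 13.
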